8.3.6.2 Time to MRD negative

The time to MRD negative status is defined as the time from randomization to first occurrence of MRD negativity. Patients without reaching MRD negative status level will be censored according to the following events:

- Patients experiencing induction failure will be censored at maximum follow-up (i.e. date of FPFV to date of LPLV used for the analysis).
- Patients not experiencing induction failure will be censored at their last adequate MRD assessment. If a patient does not have any adequate MRD assessment, patients will be censored at randomization date.

An adequate MRD assessment is considered any assessment indicating MRD status apart from 'unknown' or 'not done' or 'undetermined'. 'Undetermined'.

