7.2.1.4 Assessment of minimum residual disease (MRD) in bone marrow

For the purpose of the secondary MRD endpoint, MRD will be assessed by flow cytometry, since this technology can be used for the large majority of AML patients. Assessments will be performed at baseline during treatment phases indicated in [Table 7-1](#) and [7-3](#). Patients with leukemic blasts below 0.1% will be considered as MRD-negative based on leukemia-associated immunophenotype (LAIP). [REDACTED]

[REDACTED]

[REDACTED]

Table 7-3 Flow cytometry MRD sample collection plan

Sample Type	Volume/visit	Visit	Time Point
Bone Marrow Samples			
Bone Marrow Aspirate for flow cytometry MRD analysis	6ml* *First BMA pull should be used for this assessment	Screening	Anytime
		Induction Phase 1 Day 21-28	Pre-dose
		Induction Phase 2 Day 21-28	Pre-dose
		Consolidation phase C1 Day 21-28	Pre-dose
		Prior to 1 st cycle of Post-consolidation Phase	Pre-dose
		Post-consolidation Phase C4 Day 1	Pre-dose
		Post-consolidation Phase C7 Day 1	Pre-dose
		Post-consolidation Phase C10 Day 1	Pre-dose
		Completion of Post-consolidation Phase C12 Day 28	Pre-dose
		At relapse (at any phase of the study)	Anytime
		Post treatment Follow Up: 3 months after end of post-consolidation therapy, and at relapse	Anytime

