10.5.2.2 MRD negative status

The percentage of patients with MRD negative bone marrow will be summarized along with exact 95% CI by treatment group and by treatment phase. Importantly, comparisons of the MRD levels between the end of the consolidation phase during the post-consolidation phase will be performed by treatment groups.

The time to MRD negative status is defined as the time from randomization to first occurrence of MRD negativity. Patients without reaching MRD negative status level will be censored according to the following events:

- Patients experiencing induction failure will be censored at maximum follow-up (i.e. date of FPFV to date of LPLV used for the analysis).
- Patients not experiencing induction failure and who did not die (any cause) will be censored at their last adequate MRD assessment.

Moreover, the kinetics of MRD levels will be displayed in terms of boxplot by over time for each treatment phase.

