7.2.1 Handling of missing values/censoring/discontinuations

In the primary analysis, a patient who had not an EFS event at the date of the analysis cut-off will have his/her EFS censored at the time of the last adequate response assessment before the cut-off date.

Induction failure is defined as failure to achieve CR or CRi with adequate blood count recovery up to 93 days after start of induction phase.

A patient who failed to achieve CR or CRi without adequate blood count recovery in induction phase based on available response assessments, would have his/her EFS event documented at randomization date.

A patient who discontinued induction treatment phase without an efficacy assessment will also be considered to have failed to achieve CR or CRi with adequate blood count recovery and would have his/her EFS event at randomization date as well.

However, a patient who discontinued due to lack of efficacy in the consolidation and post-consolidation treatment phase without any supportive response assessment will be censored at the last adequate response assessment date.

EFS events documented after the initiation of HSCT or new anti-neoplastic therapy will be considered as EFS event for the primary EFS analysis.

If an EFS event is observed after two or more missing or non-adequate response assessments, then EFS will be censored at the last adequate response assessment before the EFS event. If an

EFS event is observed after a single missing or non-adequate response assessment, the actual date of event will be used. An adequate response assessment is considered any disease assessment indicating response status apart from ‘unknown’ or ‘not done’. The event and censoring times for EFS are summarized as follow:

Table 7-1 Primary EFS analysis (event date / outcome)

Situation	Options for event date	Outcome
A No baseline assessment	Randomization date	Censored
B1 Relapse at / or before next scheduled assessment date or death	Date of relapse/death	Event
B2 Relapse/death after exactly one missing assessment	Date of relapse/death	Event
B3 Relapse/death after two or more missing assessments	Date of last adequate assessment	Censored
B4 Relapse/death after HSCT or anti-neoplastic therapy	Date of relapse/death	Event
C Induction failure (incl. lack of post-baseline efficacy assessment)	Randomization date	Event
D No relapse/ no induction failure / no death	Date of last adequate response assessment	Censored

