8.3.6 Measurable Residual Disease (MRD) by flowcytometry (LAIP approach)

8.3.6.1 MRD status

MRD status will be reported for all patients as best response of MRD assessment outcome. Thus, patients who reached at least once MRD- will have their MRD status as negative. If all MRD assessment are positive or undetermined then MRD status will be reported as such.

It is acknowledged that for patients who failed induction therapy, no MRD assessment should be available. MRD status of these patients will be reported as ‘not done due to induction failure’. If patient failed induction therapy but have MRD assessment evaluated, MRD status will be reported as is in the analysis. Of note, some patients reached CR or CRi with adequate blood count recovery after 93 days after start of treatment and are considered to have failed induction therapy.

Patients completing successfully induction therapy (i.e. CR or CRi with adequate blood count recovery within 93 days after start of treatment) without MRD assessment will be reported as ‘missing’ for their status of MRD. This will be the case also for consolidation and post-consolidation until CR or CRi with adequate blood count recovery is not maintained.

The percentage of patients with MRD negative/positive/undetermined/missing (irrespective of investigator response assessment as per ELN criteria) be summarized along with exact 95% CI by treatment group and by treatment phase (i.e. Induction (I and II), consolidation and post-consolidation). If sufficient number of patients entering post consolidation, comparisons of the MRD levels between the end of the consolidation phase during the post-consolidation phase will be performed by treatment groups. Status of MRD for patients moving to HSCT and re-entering post-consolidation will be summarized prior and post HSCT.

In addition, the percentage of patients with CR and MRD-, CR with MRD+, CR and undetermined status of MRD and CR with missing MRD data will be reported by treatment groups. Similarly for CRi with adequate blood count recovery and other response categories (CRi without adequate blood count recovery, PR, etc.). Only CR and CRi with adequate blood count recovery will be counted within 93 days after start of chemotherapy will be considered.

Moreover, the kinetics of MRD levels (quantitative) will be displayed in terms of boxplot by over time for each treatment phase.

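### Time to MRD negativity: responders who die or relapse while still MRD-positive are censored at their last MRD test, which modestly overstates the conversion curve

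*SAP*

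**What the plan says.** SAP 8.3.6.2 sets the endpoint: "The time to MRD negative status is defined as the time from randomization to first occurrence of MRD negativity". It then gives three rules for patients who never reach negativity.

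- Induction failures: "Patients experiencing induction failure will be censored at maximum follow-up (i.e. date of FPFV to date of LPLV used for the analysis".
- All other patients: "Patients not experiencing induction failure will be censored at their last adequate MRD assessment".
- Those among them with no usable test: "If a patient does not have any adequate MRD assessment, patients will be censored at randomization date".

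SAP 7.2.1 fixes who belongs to the first group: "Induction failure is defined as failure to achieve CR or CRi with adequate blood count recovery up to 93 days after start of induction phase". Anyone who responds in time and later relapses or dies is therefore not an induction failure and falls under the second rule.

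Protocol 10.5.2.2 words the second rule more narrowly: "Patients not experiencing induction failure and who did not die (any cause) will be censored at their last adequate MRD assessment". It gives no rule for responders who die without MRD negativity. A responder who relapses and survives is already censored at the last test under the protocol.

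SAP 8.3.7 (neutrophil and platelet recovery) has the same structure, but it sends both deaths and induction failures to maximum follow-up. The visible text of SAP section 11 says the protocol-specified analyses were not changed. The SAP's document history mentions altered censoring for DFS and CIR only.

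**The concern.** A responder who dies MRD-positive can no longer convert. A responder who relapses cannot be seen to convert either. Protocol Table 7-3 schedules a sample "At relapse (at any phase of the study" and none after that, and protocol 7.1.4 ends study treatment at relapse. Censoring these patients assumes they would have converted at the same rate as those still under test. That is informative censoring, and it pushes 1 minus Kaplan-Meier upward.

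Induction failures in the same analysis are handled properly: they cannot convert, and they stay in the denominator. The fault is that later deaths and relapses are not treated alike.

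Time to MRD negativity is a listed between-arm secondary objective. The excess grows with the frequency of relapse and death, so the two curves are inflated unequally if those differ by arm.

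**Working it through.** The documents give no rate, event count or power for this endpoint, so there is no stated figure to reproduce. The check has four parts.

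**1. Mechanism by hand.** The estimator is 1 − ∏(1 − dⱼ/nⱼ), with dⱼ conversions among nⱼ at risk at test j. Take 1,000 patients and 59.3% response (the CR rate of 16/27 in FLT3-MN patients, protocol 1.2.1.2). That gives 593 responders and 407 induction failures. Assume 50% of responders are negative at end of induction, 10% of the rest relapse or die before the next test, and 20% of those remaining convert there.

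- End of induction: 296.5 conversions of 1,000; survival factor 0.7035; 296.5 responders still positive.
- Next test: 296.5 × 0.90 = 266.85 still testable; 266.85 × 0.20 = 53.37 conversions.
- SAP rule: at risk 407 + 266.85 = 673.85; 1 − 0.7035 × (1 − 53.37/673.85) = 35.2%.
- Relapse and death kept in the denominator: at risk 703.5; 1 − 0.7035 × (1 − 53.37/703.5) = 35.0%.
- Actual proportion converted: (296.5 + 53.37)/1,000 = 35.0%.

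One interval adds about 0.2 points, and the excess accumulates over later tests.

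**2. Simulation on the Table 7-3 schedule.** There were 40,000 patients per scenario, read at 24 months. From the documents: response 59.3% and 1-year DFS 0.60 (protocol 1.2.1.2). DFS of 0.40 is near the lower confidence limit of 0.39. Assumed: response 75% as an alternative; 30%, 50% or 70% of responders negative at end of induction; 10% or 30% converting per later test; 30% of competing events being deaths; the same relapse/death hazard whether MRD-positive or negative. That hazard is −ln(DFS)/12, i.e. 0.0426 per month for DFS 0.60 and 0.0764 for 0.40. Selected results with all patients evaluable (gaps come from unrounded values):

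| Response | 1-yr DFS | Negative at end of induction / per later test | SAP rule | Competing event | Gap |
|---|---|---|---|---|---|
| 59.3% | 0.60 | 30% / 10% | 35.4% | 33.3% | 2.2 |
| 59.3% | 0.60 | 30% / 30% | 50.1% | 47.6% | 2.5 |
| 59.3% | 0.60 | 70% / 10% | 48.6% | 48.1% | 0.5 |
| 75% | 0.40 | 30% / 30% | 60.4% | 53.7% | 6.7 |
| 75% | 0.40 | 70% / 30% | 67.5% | 65.8% | 1.7 |

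The competing-event figure equalled the crude proportion ever negative. The SAP rule was higher in all 48 scenarios run: 24 with everyone evaluable and 24 with 10% unevaluable. The second set also brings in the rule that censors at randomization, a separate matter, so its gaps are not used here.

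**3. A separate simulation.** This assumed 25% induction failure and 5%, 10% or 15% relapse or death per interval among responders not yet negative. It gave 57.8%, 57.0% and 55.3% under the SAP rule against 55.9%, 53.4% and 51.4% actually converting. The excess is 1.9, 3.6 and 3.9 points. Its conversion probabilities are not set out here, so it serves only as support for the order of magnitude.

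**4. Effect on an arm difference.** Take 59.3% response in both arms, 50% negative at end of induction, 20% per later test, and DFS of 0.60 against 0.75. The SAP rule gives 48.5% and 50.6%, a difference of 2.1 points. The competing-event version gives 47.0% and 49.6%, a difference of 2.6. In the separate simulation, setting 5% against 15% relapse or death shrinks the difference from 55.9 − 51.4 = 4.5 to 57.8 − 55.3 = 2.5 points. The difference shrinks in both cases and the ordering holds.

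**The case against.** The case for leaving this alone has real substance.

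- Neither document names the estimator for this endpoint, whereas the SAP names Kaplan-Meier for DFS, CIR and CID. This stands: the direction of bias rests on the inference that censoring rules imply a Kaplan-Meier type curve.
- The conversion rates are assumed, and the full test schedule is unlikely to have been realised, because SAP section 1 says most patients left within weeks of the futility stop. This also stands. When 70% of responders are negative at end of induction, the gap is only 0.5 to 1.7 points. In the other direction, protocol 2.4 describes a strong link between MRD and relapse. The equal-hazard assumption may therefore understate losses among MRD-positive responders.
- SAP 8.3 makes the secondary efficacy analyses descriptive, without p-values, in a trial already stopped. No decision turns on this curve.

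Three stronger readings are tempting but unsupported. A reader might infer that the reported MRD-negative percentage is inflated. It is not: under SAP 8.3.6.1 "patients who reached at least once MRD- will have their MRD status as negative", with no censoring involved. A reader might infer that the SAP introduced the censoring of relapses. The protocol limit concerned death only, and relapsed survivors were already censored at the last test. A reader might also infer that the rule could reverse an arm comparison. The calculations show attenuation only.

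**Conclusion.** The point holds as a minor one. As written, SAP 8.3.6.2 removes from the risk set responders who die or relapse while MRD-positive. This conflicts with its own treatment of induction failures and with the treatment of deaths in 8.3.7. It also drops the protocol's death limit without a visible declaration. The protocol text is itself incomplete, so the SAP filled a gap and did not displace a correct rule.

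Given a Kaplan-Meier type estimator, the overstatement is 0.5 to 2.5 points at 59.3% response and 1-year DFS of 0.60. It reaches 6.7 points at 75% response and DFS of 0.40, and is about 2 to 4 points in the separate simulation. All of these depend on assumed conversion rates. An arm difference may be attenuated if relapse or death differs by arm.

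The SAP says decisions on the final analysis were made after unblinding, and a reader might infer that the death limit was removed in the light of the data. The documents do not show which SAP version dropped it, so they do not support that inference. They support only the need to record the change.

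**What to change.** In SAP 8.3.6.2:

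- Treat relapse or death before MRD negativity as a competing event. Either use a cumulative incidence function or censor these patients at maximum follow-up, as is done for induction failures and, for deaths, in 8.3.7.
- Censor at the last adequate MRD test only patients who are alive and in remission.
- Name the estimator.
- Record the departure from protocol 10.5.2.2 in section 11.

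Labelling the events as competing is not enough. SAP Tables 8-4 and 8-5 do that for CIR and CID and still censor them under Kaplan-Meier.

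The cost is about one sentence on censoring, one flag in the derivation, the estimator's name and a line in section 11. No new data are needed.

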8.3.6.3 Duration of MRD negative

The duration of MRD- will be derived only for patients who reached MRD- and is defined from first occurrence of MRD – to MRD +, relapse or death whichever occurs first.

Patients without MRD+, relapse from CR nor death will be censored at last adequate MRD assessment.

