4.2.4 Follow-up phase

Patients who discontinue study treatment will continue to have response assessments performed every 12 weeks until documented relapse, and thereafter will be followed every 3 months for survival except those who are lost to follow-up. Data on anti-neoplastic therapies will be collected as well.

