7.1.7 Follow up for efficacy evaluations

Patients who discontinue study treatment for reasons other than death, failure to achieve CR or CRi with adequate blood count recovery in the induction phase or relapse from CR or CRi with adequate blood count recovery will continue to have post-treatment assessments as outlined in [Section 7.1](#) until relapse or death.

During this phase, the following data will be collected:

- Antineoplastic therapy/transplantation after discontinuation of treatment: every 3 months including start of new line, best response, and relapse date etc...

The following assessments will be performed:

- Physical examination for extramedullary disease assessment, blood samples for hematology [REDACTED]: every 3 months
- Bone marrow aspirate/biopsy for disease assessment [REDACTED]: after first 3 months after completion of post-consolidation therapy and at relapse.
- Questionnaires (EQ5D-5L, FACT with FACT-Leu) [REDACTED] every 6 months during the first two years and then yearly.

Patients will be followed in post-treatment follow up until relapse or end of study, whichever occurs first.

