7.1.8 Survival follow up

Patients will enter the survival follow-up phase once they complete the safety follow up period (30 days after the last dose of midostaurin/placebo) in case of induction failure or have relapse during post-treatment follow-up. Patients will then be contacted by telephone every 3 months +/- 2 weeks or have a visit to follow up on their survival status. Any new antineoplastic medications that have been started since the last contact date will also be collected during these phone calls or visits.

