8.3 Analysis of secondary endpoints

The secondary efficacy variables include CR or CRi with adequate blood count recovery rate, MRD, DFS, CIR and CID. The assessment of these endpoints, except MRD, will be based on the IWG criteria for AML [[Cheson et al 2003](#), [ELN 2017 / Döhner et al 2017](#)] as per investigator assessment. All these endpoints will only be descriptively summarized with 95% CIs but without any p-values.

The rate of CR/CRi with adequate blood count recovery will be analyzed based on the FAS. However, DFS, Cumulative Incidence of Relapse (CIR) and Cumulative Incidence of Death (CID) will be analyzed based on data from responders (CR or CRi with adequate blood count recovery within 93 days after start of treatment) in the FAS. Assessment of relapse from CR or CRi with adequate blood count recovery, DFS, CIR and CID will not consider whether a patient received HSCT. All secondary analyses will include all data observed up-to the cut-off date, unless otherwise specified.

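### After the last MRD test, SAP 8.3.6.3 keeps a patient at risk only if an event is later recorded, so a Kaplan-Meier estimate of MRD-negative duration is biased downward

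*SAP*

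**What the plan says.** **Event.** SAP 8.3.6.3 measures from the first MRD-negative result to MRD positivity, "relapse or death whichever occurs first". It sets no maximum gap between the last MRD test and the event.

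**Censoring.** "Patients without MRD+, relapse from CR nor death will be censored at last adequate MRD assessment". Under SAP 8.3.6.2, an adequate MRD assessment is one that yields a determined MRD status, so response visits and survival calls do not count.

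**MRD sampling.** Protocol Table 7-3 (section 7.2.1.4) ties flow-cytometry samples to the treatment phases. The last entry reads "Post treatment Follow Up: 3 months after end of post-consolidation therapy, and at relapse". After that sample, or after early treatment discontinuation, a further MRD test is expected essentially only at relapse.

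**Relapse and death.** Protocol 4.2.4: "Patients who discontinue study treatment will continue to have response assessments performed every 12 weeks until documented relapse". Protocol 7.1.7: "Patients will be followed in post-treatment follow up until relapse or end of study, whichever occurs first". Protocol 7.1.8, on survival: "Patients will then be contacted by telephone every 3 months +/- 2 weeks". SAP 8.3 adds: "All secondary analyses will include all data observed up-to the cut-off date, unless otherwise specified".

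**Neighbouring endpoints.** DFS (SAP 8.3.3) censors event-free patients at the last adequate response assessment, the visit series that finds relapse. EFS (SAP 7.2.1) censors events that follow two or more missing assessments. Section 8.3.6.3 has neither safeguard.

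**The concern.** Kaplan-Meier estimation needs censoring that carries no information about the later outcome. Here two follow-up series are mixed. Events come from response and survival follow-up, which continue. Censoring dates come from MRD sampling, which stops. Once a patient's sampling has ended, that patient's membership of the risk set is decided by whether an event is recorded afterwards.

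At stake is the reported durability of MRD negativity. It would look shorter than it was because of the rule, not because of the patients. Early discontinuation makes this worse, because MRD sampling then ends sooner while relapse and death can still be recorded.

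**Working it through.** The documents give no figure for this endpoint, so there is nothing to reproduce. The check has four steps.

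**1. The mechanism on two records.** Both patients become MRD-negative at month 1, have their last MRD test at month 5 and stop treatment. Patient 1 relapses at month 16. Patient 2 is in remission at a response visit at month 30.

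| | Patient 1 | Patient 2 | At risk at month 16 | Kaplan-Meier after month 16 |
|---|---|---|---|---|
| SAP rule | event, month 16 | censored, month 5 | 1 | 1 − 1/1 = 0 |
| Censor at last response assessment | event, month 16 | censored, month 30 | 2 | 1 − 1/2 = 0.50 |

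**2. When scheduled sampling ends.** Assume first MRD negativity at the end of induction 1, four consolidation cycles, twelve 28-day post-consolidation cycles (336 days) and one sample 91 days later.
- 28-day consolidation cycles: 112 + 336 + 91 = 539 days, or 17.7 months.
- 35-day cycles: 140 + 336 + 91 = 567 days, or 18.6 months.
- 50-day cycles (the protocol maximum): 200 + 336 + 91 = 627 days, or 20.6 months.

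**3. Follow-up available before the stop.** Protocol Amendment 1, dated 08-Jun-2018, states that no patient had yet been enrolled. The SAP Introduction gives 23-Sep-2019 as the stop date. That is 365 + 107 = 472 days, or 15.5 months. The first on-treatment MRD sample is at day 21 to 28, so a patient who left at the stop had at most about 15 months from first MRD negativity. That is short of the last scheduled test in step 2.

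**4. Size, by simulation.** Event times are exponential with median m, so the true value is S(t) = 0.5^(t/m). The medians, follow-up ranges and rates of early treatment stopping are assumptions; the documents give none of them.

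*Short follow-up, uniform 0–15 months, estimate at 12 months:*

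| m (months) | Early stopping per month | SAP rule | Response-assessment censoring | Gap |
|---|---|---|---|---|
| 18 | 0 | 0.55 | 0.59 | 4 points |
| 30 | 0 | 0.70 | 0.73 | 3 points |
| 18 and 30 | 0.03 | | | 9–11 points |

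Across the early-stopping rates examined, the gap is about 3 to 13 points.

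A variant without MRD conversion before relapse used follow-up of 3–15 months, m = 24 and response visits every 3 months. At stopping rates of 0, 0.03 and 0.06 per month, the SAP rule gives 0.64, 0.58 and 0.51 at 12 months. Response-assessment censoring gives 0.65, 0.66 and 0.65. The gaps are 1, 8 and 14 points. The truth is 0.5^(12/24) = 0.71, so the repaired rule also stays 5 to 6 points low here. A relapse or death between visits counts at its own date, while an event-free patient goes back to the last visit.

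*Long follow-up, uniform 20–58 months, m = 24, stopping 0.03 per month, no MRD conversion modelled:*

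| Month | SAP rule | Response-assessment censoring | Truth |
|---|---|---|---|
| 18 | 0.55 | 0.59 | 0.59 |
| 24 | 0.36 | 0.50 | 0.50 |
| 36 | 0.12 | 0.34 | 0.35 |

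A separate run gave 0.38 at month 24 under the SAP rule against 0.50, so the gap there is 12 to 14 points. With this follow-up, the bias up to month 18 is nil without early stopping and at most about 9 points at 0.06 per month.

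**The case against.** The strongest reply is that the point concerns a minor endpoint in a stopped trial. Much of that stands. Section 8.3.6.3 says only that the duration will be derived; it names no estimator, median or hazard ratio. Duration of MRD negativity is not among the objectives in SAP section 2, and SAP 8.3 restricts the secondary endpoints to descriptive summaries without p-values. A plain listing of durations would not show the bias.

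The futility stop also limits the size. A reader might infer that it made matters worse, because most patients left. The SAP Introduction says that most discontinued from the study within weeks. For them, MRD sampling and relapse follow-up largely ended together, so gaps as long as those in the two-record example do not describe them.

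It can also be said that censoring at the last assessment able to verify the state is standard. That holds when events are limited to the same assessment series. Here relapse and death come from series that run on after it.

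Two further inferences go too far. One is that the curve must fall to zero. That needs at least one relapse or death recorded after sampling has ended for the event-free patients. The other is that the comparison between arms is biased. The SAP specifies no such comparison for this endpoint, and the documents give no early-stopping rates by arm.

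**Conclusion.** The flaw is real and follows from the wording of the rule, without any modelling assumption: after the last MRD test, remaining at risk depends on a future event. If a Kaplan-Meier estimate is produced, it is biased downward.

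The size does rest on assumptions, namely exponential times and assumed rates of early stopping. It is about 3 to 13 percentage points at 12 months, measured against response-assessment censoring, with the short follow-up expected after the futility stop. Gaps of 10 points or more at 24 months arise only where follow-up runs past the last scheduled MRD test, which applies at most to the minority who continued. Neither the EFS and OS conclusions nor the futility decision is affected.

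**What to change.** Amend SAP 8.3.6.3 so that patients without MRD positivity, relapse or death are censored at the last adequate response assessment, as DFS already does. Show the curve only up to the last scheduled MRD sample, 3 months after post-consolidation, and name the estimator. On the assumptions in step 2, that limit falls 17.7 to 20.6 months after first MRD negativity.

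The cost is one sentence and one censoring date in one program; no new data are needed. The downside is small: after a patient's last MRD test, the endpoint reflects relapse and death only. The milder between-visit asymmetry that DFS already has would remain.

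Two tempting alternatives do not work:
- **Keep the present censoring date and drop events that follow a missed scheduled sample.** After the final sample none is due, so late events still count. With m = 18 and follow-up of 12–30 months, the 24-month estimate was 0.15 against a true 0.40, the same as under the SAP rule.
- **Count events only within 6 months of the last MRD test.** This gave 0.05 against 0.50 at 24 months with m = 24.
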